	
increase in the measured Hb response. Although CYP2C8 induction studies were not performed, co-administration of daprodustat with an inducer of CYP2C8 (e.g., rifampin/rifampicin) may decrease the exposure of daprodustat.
 
Even though co-administration of daprodustat with strong inhibitors and inducers of CYP2C8 is prohibited, inadvertent co-administration may occur. Due to the known time delay in enhancing erythropoiesis by daprodustat, co-administration with strong CYP2C8 inhibitors for up to 14 days is not anticipated to lead to immediate marked increases in hemoglobin levels. Therefore, there is adequate time to change to alternate therapy that does not inhibit CYP2C8.
 
Additionally, as the time for maximum induction of CYP2C8 occurs after approximately 10-14 days of dosing with rifampin (Brodie, 2013; Ohnhaus, 1989), daprodustat systemic exposure will decrease over time which will result in a lag period before an effect on Hgb is recognized and is of clinical concern.
 
Daprodustat is an inhibitor of CYP2C8: A clinical drug interaction study between 25mg and 100mg daprodustat with a CYP2C8 substrate (i.e., pioglitazone) showed that there is no PK interaction at these doses of daprodustat.
 
Daprodustat is a substrate of Breast cancer resistance protein (BCRP): Population PK analysis from Phase 2 studies suggested that while BCRP inhibitors were a covariate for daprodustat apparent total body clearance (CL/F) (8.6% lower clearance) the predicted change in exposure was not considered to be of clinical relevance.
 
Daprodustat is an inhibitor of organic anion transporter polypeptides (OATP)1B1/1B3: A clinical drug interaction study between 25mg and 100mg daprodustat with an OATP1B1/1B3 substrate (i.e., rosuvastatin) showed no PK interaction at these doses of daprodustat.
	
dose is changed, Hgb should be monitored every 4 weeks Specific guidance on the management of potential drug-drug interactions and concomitant medications is provided in Section 7.2
 
 • Hgb will be closely monitored throughout the dosing period as outlined in the SoA (See Section 2) • Specific guidance for dose adjustment, dose interruption, or discontinuation of daprodustat based on achieved Hgb is provided in Section 7.2. • Instream monitoring of safety data by internal safety review team

Potential Risk of Clinical Significance	Summary of Data/Rationale for Risk	Mitigation Strategy

Cyst progression in patients with autosomal dominant polycystic kidney disease (ADPKD)
	
Published data provide in vivo evidence for a potential role of HIF-1a in the growth of polycystic kidneys; Hif-1a deletion was sufficient to significantly mitigate a progressive polycystic phenotype in an ADPKD mouse model, while conversely pharmacologic HIF-1a stabilization was sufficient to convert a mild polycystic disease into a severely aggravated phenotype with marked loss of renal function (Kraus, 2018; Hofherr, 2018).
 
A review of the non-clinical data from toxicity studies conducted with daprodustat does not indicate an exacerbation in incidence or severity of kidney cysts in daprodustat-treated animals in comparison to controls. However, the wild type animals used in these toxicity studies have a very low background incidence of renal cysts and are not comparable to the mice used in the Kraus article (Kraus, 2018) which are an inducible kidney epithelium-specific Pkd1-deletion model.
 
There is limited experience with daprodustat in subjects with ADPKD in completed clinical trials. In the Japan phase 3 study in non-dialysis subjects, there were 5 subjects with ADPKD (all CKD stage 5) in each treatment group. Mean baseline eGFR was 10 mL/min/1.73m² in the daprodustat subjects vs. 16 mL/min/1.73m² in the rhEPO subjects. The mean (SD) percent change from baseline at Week 52 in eGFR was: -18% (8) vs. -21% (14) in daprodustat vs. rhEPO, respectively.
 
Following review of clinical data received to date, this has not been identified as a safety concern for daprodustat.
	
 • Kidney function will be monitored throughout the dosing period as outlined in the SoA (Section 2). • Monitoring of emerging safety data by an internal GSK Safety Review Team.
Other		

Darbepoetin alfa (Control)
	
See risks outlined in table for daprodustat for excessive erythropoiesis (polycythemia) leading to thrombosis and/or tissue ischemia; Death, MI, stroke, heart failure, thromboembolic events, thrombosis of vascular access; and for increased cancer-related mortality and tumor progression.
 
Uncontrolled hypertension.
 
Pure red cell aplasia.
	
 • See mitigation strategies outlined in table for daprodustat for Excessive erythropoiesis (polycythemia) leading to thrombosis and/or tissue ischemia; Risk of death, MI, stroke, heart failure, throboembolic events, thrombosis of vascular access; and for Increased cancer-related mortality and tumor progression. • Specific eligibility criteria related to current uncontrolled hypertension are outlined in Section

Potential Risk of Clinical Significance	Summary of Data/Rationale for Risk	Mitigation Strategy
		
6.2
 
 • Specific eligibility criteria related to personal history of pure red cell aplasia are outlined in Section 6.2
Challenge Agents		
Acetylcholine	Acetylcholine stimulates the production by the vascular endothelium of nitric oxide, a potent vasodilatory agent. Distribution of acetylcholine to the peripheral vasculature has the potential to lead to a decrease in blood pressure; however acetylcholine is rapidly metabolized by acetylcholinesterase, minimizing the potential for pharmacological concentrations distant from the infusion site.	
 • Study undertaken only at specialist centers by experienced study personnel trained to conduct forearm blood flow assessment • Patients monitored continuously throughout technique • Minimum dose given for required physiological response • Patients with recent cardiovascular events excluded from the study
N-monomethyl-L-arginine (NMMA)	L-NMMA inhibits nitric oxide synthase, leading to decreased production of nitric oxide, which can lead to increases in blood pressure.	
 • Study undertaken only at specialist centers by experienced study personnel trained to conduct forearm blood flow assessment • Patients monitored continuously throughout technique • Minimum dose given for required physiological response • Patients with recent cardiovascular events excluded from the study
Sodium nitroprusside	Sodium nitroprusside directly causes vasodilation leading to decreases in blood pressure. Reported side effects of sodium nitroprusside administration are excessive hypotension and excessive accumulation of cyanide at high rates of infusion.	
 • Study undertaken only at specialist centers by experienced study personnel trained to conduct forearm blood flow assessment • Patients monitored continuously throughout technique • Minimum dose given for required physiological

Potential Risk of Clinical Significance	Summary of Data/Rationale for Risk	Mitigation Strategy
		response 
 • Patients with recent cardiovascular events excluded from the study
Study Procedures		
Venous occlusion plethysmography	Primary risk associated with venous venous occlusion plethysmography is related to the cannulation of the brachial artery. This has the potential for causing damage to the brachial artery, thrombosis, digital ischemia, and hemorrhage, as well as discomfort at the infusion site.	
 • Study undertaken only at specialist centers by experienced study personnel trained to conduct forearm blood flow assessment • Cannulation of the brachial artery for infusion of the challenge agents will be done with a fine (27 gauge) needle to minimize any injury to the artery • Cannulation will be done under a local anesthetic to minimize participant discomfort

References

- Campochiaro PA. Ocular versus extraocular neovascularization: mirror images or vague resemblances. *Invest Ophthalmol Vis Sci*. 2006; 47:462-74.
- Hofherr, A., *et al*, *HIF-1α drives cyst growth in advanced stages of autosomal dominant polycystic kidney disease*; *Kidney International* (2018) 94, 849–851.
- Kraus, A., *et al*, *HIF-1α promotes cyst progression in a mouse model of autosomal dominant polycystic kidney disease*; *Kidney International*, 2018.

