2. SCHEDULE OF ACTIVITIES (SOA)

Procedure	Screening ¹	Treatment Period ²						Follow-up ³
	Up to 30 Days	Day 1	Repeat Day 1 ¹⁷	Day 14	Day 28	Day 42	Repeat Day 42 ¹⁷	
Informed consent	X							
Eligibility Criteria	X	X ⁴						
Physical examinations, Medical History, Demographics	X	X ⁵						
HemoCue Hgb	X	X ⁶	X	X	X	X	X	
eGFR	X							
Vital signs	X	X ⁶	X	X	X	X	X	X
Clinical chemistry ⁷	X					X		X
Hematology ⁷	X	X		X	X	X		X
Serum pregnancy test (FRP only)	X							
Urine pregnancy test (FRP only) ⁸		X	X	X	X	X	X	X
Folate & Vitamin B ₁₂	X							
12 Lead ECG	X	X ⁶				X		X
Ferritin & TSAT	X							
hs-CRP	X	X				X		
Females only: FSH ⁹	X							
Brachial artery palpation	X							
Randomization		X						
Daprodustat administration ¹⁰		<=====>						
Darbepoetin alfa administration ¹⁰		X ¹⁰		X	X	See footnote 18		
Study treatment adjustment ¹¹					X			
Liver chemistry monitoring				X	X			
International Normalized Ratio (INR) ¹²	X	X	X			X	X	

Procedure	Screening ¹	Treatment Period ²						Follow-up ³
	Up to 30 Days	Day 1	Repeat Day 1 ¹⁷	Day 14	Day 28	Day 42	Repeat Day 42 ¹⁷	
Hepatitis B and C screening ¹³	X							
HbA1c, lipids ⁷		X						
Forearm Blood Flow (FBF) ¹⁴		X	X			X	X	
Pulse Wave Velocity (PWV) ¹⁴		X	X			X	X	
AE and SAE Assessment	X ¹⁵	X	X	X	X	X	X	X
Blood draw for storage biomarkers ¹⁶		X				X		
Review concomitant medications	X	X	X	X	X	X	X	X

¹All participants will undergo screening assessments within 30 days of enrolment.

²Allowable time window \pm 2 days except for the forearm blood flow (FBF) & pulse wave velocity (PWV) as noted.

³Allowable time window \pm 3 days. Follow up will occur 7-14 days \pm 3 following completion of the last FBF procedure. See Section 8.2 for guidance regarding EW participants.

⁴Eligibility criteria to be assessed prior to performance of the FBF procedure include HemoCue hemoglobin (Hgb), vital signs & 12-lead electrocardiogram (ECG).

⁵Only a brief physical exam on Day 1.

⁶As detailed in Exclusion Criteria (Section 6.2).

⁷Clinical chemistry, hematology and other laboratory tests as listed in Appendix 2.

⁸Local urine pregnancy testing will be standard for protocol unless serum testing is required by local regulations or Institutional Review Board (IRB)/ Independent Ethics Committee (IEC).

⁹As detailed in Inclusion Criteria (Section 6.1).

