¹⁰The initial dose of study treatment will be given **after** the completed Day 1/Repeat Day 1 FBF & PWV procedures. Participants will receive **EITHER** daprodustat **OR** darbepoetin alfa. The final dose of daprodustat will be Day 41 (i.e., the day prior to the FBF & PWV procedures), while the final dose of darbepoetin alfa will be Day 28. If repeat procedures are needed the dosing will be extended (See Section 9.6.1.4).

¹¹See Section 7.2 for details on study treatment adjustment

¹²Applies only to participants on anti-coagulant therapy; further details concerning measurement of the international normalised ratio (INR) and subsequent actions can be found in the study reference manual (SRM).

¹³If test otherwise performed within 3 months prior to first dose of study treatment, testing at screening is not required

¹⁴The FBF & PWV assessments are to be performed following confirmation of INR < 3.0 for participants on anticoagulant therapy. The Day 42 FBF & PWV assessments can be delayed up to 1 week (i.e., Day 49), while randomization (Day 1) should be delayed until the participant's INR < 3.0 (Section 9.6.1.1).

¹⁵Only serious adverse events (SAEs) assessed as related to study participation are collected at this visit. See Appendix 4 for additional details.

¹⁶As described in Section 9.8

¹⁷Indicates the procedures to be performed on the repeat visits only if the visit is deemed necessary. See Section 9.6.1.4

¹⁸Darbepoetin is only to be given on Day 42 if a Repeat Day 42 is needed.

- The timing and number of planned study assessments, including: safety, pharmacodynamic or other assessments may be altered during the course of the study based on newly available data (e.g., to obtain data closer to the time of peak plasma concentrations) to ensure appropriate monitoring.
- Any changes in the timing or addition of time points for any planned study assessments must be documented and approved by the relevant study team member and then archived in the sponsor and site study files, but will not constitute a protocol amendment. The IRB/IEC will be informed of any safety issues that require alteration of the safety monitoring scheme or amendment of the ICF.

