12.2. Appendix 2: Clinical Laboratory Tests

All study-required laboratory assessments will be performed by a central laboratory with the exception of HemoCue Hgb, INR measurements and urine pregnancy tests which will be performed at the clinical site. The results of each HemoCue Hgb must be entered into the participant's eCRF.

A local Hematology lab will be allowed in the event that central labs are unavailable.

Tests included in [Table 4](#) must be conducted in accordance with the Laboratory Manual and Study Protocol SoA (See [Section 2](#)). Laboratory requisition forms must be completed and samples must be clearly labeled with the participant number, protocol number, site/centre number, and visit date. Details for the preparation and shipment of samples will be provided by the laboratory and are detailed in the SRM. Reference ranges for all safety parameters will be provided to the site by the laboratory responsible for the assessments.

Refer to the SRM for appropriate processing and handling of samples.

Table 4 Protocol Required Laboratory Assessments

Laboratory Assessments	Parameters		
Hematology	Platelet count	RBC indices:	WBC count with Differential
	RBC count	MCV	Neutrophils
	Reticulocyte count	MCH	Lymphocytes
	Hgb	MCHC	Monocytes
	Hematocrit	RDW	Eosinophils
	WBC count (Absolute)		Basophils
Clinical Chemistry¹	Sodium (serum)	AST ¹	Carbon Dioxide (total)
	Potassium (serum)	ALT ¹	Albumin
	Creatinine (serum)	Chloride (serum)	Urea (serum)
	Glucose	Bilirubin (total and direct/indirect)	Alkaline Phosphatase
Other laboratory tests	Serum ferritin	TSAT	hs-CRP
	Total cholesterol	LDL-C (direct)	HDL-C
	Triglycerides	Serum/Urine hCG pregnancy test ²	FSH ³
	HbA1c	Folate	Vitamin B ₁₂
	Serology (hepatitis B surface antigen [HBsAg], and hepatitis C virus antibody)		

Abbreviations: RBC: red blood cells, WBC, white blood cells; MCV, mean corpuscular volume; MCH, mean corpuscular hemoglobin; MCHC, mean corpuscular hemoglobin concentration; RDW, red blood cell distribution width, AST, aspartate transaminase; LDL-C, low density lipoprotein-C; HDL-C, high density lipoprotein-C, hCG= human chorionic gonadotropin.

¹Details of Liver Chemistry Stopping Criteria and Required Actions and Follow-Up Assessments after liver stopping or monitoring event are given in Section 8.1.1 and Section 12.6.

²For females of reproductive potential only.

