
MONITORING:
 
For bilirubin or INR criteria:
 
 Repeat liver chemistries (include ALT, AST, alkaline phosphatase, bilirubin) and perform liver event follow up assessments within 24 hrs Monitor subjects twice weekly until liver chemistries resolve, stabilize or return to within baseline A specialist or hepatology consultation is recommended 
For All other criteria:
 
 Repeat liver chemistries (include ALT, AST, alkaline phosphatase, bilirubin) and perform liver event follow up assessments within 24-72 hrs Monitor subjects weekly until liver chemistries resolve, stabilize or return to within baseline 	
form including acetaminophen, herbal remedies, other over the counter medications.
 
 Record alcohol use on the liver event alcohol intake case report form 
For bilirubin or INR criteria:
 
 Anti-nuclear antibody, anti-smooth muscle antibody, Type 1 anti-liver kidney microsomal antibodies, and quantitative total immunoglobulin G (IgG or gamma globulins). Serum acetaminophen adduct HPLC assay (quantifies potential acetaminophen contribution to liver injury in subjects with definite or likely acetaminophen use in the preceding week [James, 2009]). Liver imaging (ultrasound, magnetic resonance, or computerised tomography) and /or liver biopsy to evaluate liver disease: complete Liver Imaging and/or Liver Biopsy CRF forms.
---	---

¹ Serum bilirubin fractionation should be performed if testing is available. If serum bilirubin fractionation is not immediately available, discontinue study treatment for that subject if ALT \geq 3xULN and bilirubin \geq 2xULN. Additionally, if serum bilirubin fractionation testing is unavailable, **record presence of detectable urinary bilirubin on dipstick**, indicating direct bilirubin elevations and suggesting liver injury.

² All events of ALT \geq 3xULN and bilirubin \geq 2xULN (>35% direct bilirubin) or ALT \geq 3xULN and INR > 1.5, if INR measured which may indicate severe liver injury (possible 'Hy's Law'), **must be reported as an SAE (excluding studies of hepatic impairment or cirrhosis)**; INR measurement is not required and the threshold value stated will not apply to subjects receiving anticoagulants

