12.7. Appendix 7: Risk Assessment

Potential Risk of Clinical Significance	Summary of Data/Rationale for Risk	Mitigation Strategy
Daprodustat		
Excessive erythropoiesis leading to thrombosis and/or tissue ischemia	
In animal studies, excessive erythropoiesis (Hgb/Hct > upper limit normal) attributed to daprodustat was associated with vascular congestion/inflammation, microthrombi, and tissue ischemia in a number of organs.
 
In the phase 2 proof of concept study, a high incidence of discontinuation due to hemoglobin stopping criteria (Hgb > 13.5 g/dL or Hgb increased > 1 g/dL over any 2-week period) was observed. In non-dialysis subjects administered 10 mg, 25 mg, 50 mg or 100 mg of daprodustat daily, a total of 21 of 61 subjects (34%) met these criteria. In hemodialysis-dependent subjects administered either 10 mg or 25 mg of daprodustat daily, a total of 8 of 31 subjects (26%) met these criteria.
 
Phase 2 dose-ranging studies, and associated statistical and exposure response modelling has informed Phase 3 dose rationale, starting doses, dose levels, and dose adjustment scheme to optimize Hgb management.
 
Integrated AE data [including 2 global phase 2b studies (24-week treatment duration) and 2 Japanese phase 3 studies (52-week treatment duration)]: Few subjects experienced a possible thrombosis related adverse event in the setting of excessive erythropoiesis [3/688 (0.5%) subjects on daprodustat vs. 0/404 on rhEPO].
 
Following review of clinical data received to date, this has not been identified as a safety concern for daprodustat when dose is managed appropriately according to target Hgb. However, experience with daprodustat is currently insufficient to fully characterize this risk.
	
 • Specific eligibility criteria related to requirements for entry Hgb are detailed in Section 6.1 • Hgb will be closely monitored throughout the dosing period as outlined in the SoA (See Section 2) • Specific guidance for dose adjustment, dose interruption, or discontinuation of daprodustat based on achieved Hgb (including rate of change) is provided in Section 7.2 and Section 8.1 • Instream monitoring of safety data by internal safety review team

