Worsening hypertension	In a dog cardiovascular study, single oral doses of daprodustat (up to 90 mg/kg) did not produce effects on blood pressure.	
 • Specific eligibility criteria related to blood pressure, including exclusion of subjects with uncontrolled hypertension, are detailed in

Potential Risk of Clinical Significance	Summary of Data/Rationale for Risk	Mitigation Strategy
	
Marketed rhEPO and its analogues have been associated with risks related to uncontrolled hypertension, including the need for initiation of or increases in antihypertensive therapy when used in patients with anemia of CKD (i.e. 25% Epogen, 27% Mircera, and 40% Aranesp treated patients with renal anemia required initiation or increase in their anti-hypertensive medications; hypertensive encephalopathy and seizures have been reported. The contribution of rhEPO-associated hypertension to the unfavourable effects on cardiovascular outcomes remains uncertain).
 
Integrated AE data from clinical trials with daprodustat [including 2 global phase 2b studies (24-week treatment duration) and 2 Japanese phase 3 studies (52-week treatment duration)]:
 
 ○ The majority (>90%) of subjects had baseline history of hypertension. ○ No meaningful difference was seen between treatment groups in AEs (preferred term) of "hypertension" [29/688 (4%) daprodustat vs. 19/404 (4%) rhEPO; 0.91 relative risk (RR) (95% confidence interval: 0.5, 1.67)] or "blood pressure increased" [16 (2%) daprodustat vs. 7 (2%) rhEPO; RR 1.22 (0.48,3.11)]. Results were not substantively different between non-dialysis and haemodialysis subjects. ○ Although no clinically meaningful changes in blood pressure were observed, subjects in both treatment groups required increases in anti-HTN medications: 
 ○ In the 24-week global phase 2b studies, 25/170 (15%) of ND subjects receiving daprodustat vs. 18/80 (14%) control and 22/177 (12%) of HD subjects receiving daprodustat vs. 2/39 (5%) control. ○ In the 52-week Japan phase 3 studies, 57/149 (38%) of ND subjects receiving daprodustat vs. 68/150 (45%) rhEPO and 51/136 (38%) of HD subjects receiving daprodustat vs. 66/135 	
Section 6.2
 
 • Blood pressure will be closely monitored throughout the dosing period as outlined in the SoA Table Section 2. • Monitoring of emerging safety data by an internal GSK Safety Review Team.

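### Appendix 7 relies on kidney function monitoring throughout dosing, but the schedule has no kidney measure between screening and Day 42, the day after the last planned daprodustat dose

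*Protocol*

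**What the plan says.** The ADPKD row of Protocol Appendix 7 (Section 12.7) offers two mitigations. The one that acts on the individual participant is "Kidney function will be monitored throughout the dosing period as outlined in the SoA (Section 2". The other is the sponsor's own review of emerging safety data.

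The Schedule of Activities (Protocol Section 2, repeated in SAP Section 10.2.1) has three relevant rows:

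- eGFR: screening only.
- "Clinical chemistry": screening, Day 42 and follow-up. Appendix 2, Table 4 places serum creatinine and urea in this panel and in no other.
- "Liver chemistry monitoring": Days 14 and 28.

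Footnote 10 to the schedule fixes the end of treatment: "The final dose of daprodustat will be Day 41 (i.e., the day prior to the FBF & PWV procedures").

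Appendix 7 uses nearly the same wording for two other risks. For excessive erythropoiesis it says "Hgb will be closely monitored throughout the dosing period as outlined in the SoA (See Section 2"), and for hypertension "Blood pressure will be closely monitored throughout the dosing period as outlined in the SoA Table Section 2".

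The exclusion criteria (Section 6.2) do not name ADPKD, and Section 6.1 admits CKD stages 3 to 5, so participants with ADPKD can enter.

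**The concern.** A risk table is read as a statement of what protects participants. Here the named protection points to a schedule that does not contain it. If kidney function fell in the six weeks of daprodustat, the first scheduled result able to show it would come after the last planned dose, too late to inform a decision to stop.

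The row itself gives reasons to take the check seriously. It cites mouse work in which pharmacological HIF-1a stabilization worsened polycystic disease and renal function. It notes that the animals in the sponsor's toxicity studies are not comparable with that model. It describes limited human experience, including 5 ADPKD subjects per group in the Japanese non-dialysis study.

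This is a safety-monitoring matter. Nothing in the forearm blood flow analysis depends on it.

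**Working it through.** There is no sample size or power figure to reproduce. The check compares the schedule with the promise, visit by visit, and then counts days.

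**Scheduled measures (Protocol Section 2)**

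| Measure | Screening | Day 1 | Day 14 | Day 28 | Day 42 | Follow-up |
|---|---|---|---|---|---|---|
| Hemoglobin (HemoCue and/or hematology) | yes | yes | yes | yes | yes | yes |
| Blood pressure (vital signs) | yes | yes | yes | yes | yes | yes |
| Creatinine and urea (clinical chemistry) | yes | no | no | no | yes | yes |
| eGFR | yes | no | no | no | no | no |
| Liver chemistry | no | no | yes | yes | no | no |

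Day 1 bloods are hematology, hs-CRP, HbA1c and lipids, plus INR for participants on anticoagulants. None is a kidney measure. For Days 14 and 28, the nearest description of the liver panel is in Appendix 6: "liver chemistries (include ALT, AST, alkaline phosphatase, bilirubin"). It contains no kidney analyte. The Repeat Day 42 visit also has no clinical chemistry, although daprodustat continues up to that visit if the procedure is repeated (Section 9.6.1.4).

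**Coverage of the four planned treatment-period visits (Days 1, 14, 28, 42)**

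- Hemoglobin: 4 of 4.
- Blood pressure: 4 of 4.
- Kidney function: 1 of 4 (Day 42).
- Kidney measures on planned daprodustat dosing days (Day 1 to Day 41): 0.

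**Time without a scheduled kidney measure**

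- From Day 1 to the first on-study value: 42 − 1 = 41 days.
- Between consecutive scheduled values: screening may be up to 30 days before Day 1, so up to 30 + 41 = 71 days.
- From the last planned daprodustat dose to the first on-study value: 42 − 41 = 1 day. For darbepoetin alfa (last planned dose Day 28): 42 − 28 = 14 days.

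**With creatinine added at Days 1, 14 and 28**

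- Intervals: 14 − 1 = 13, 28 − 14 = 14 and 42 − 28 = 14 days, so the longest gap within treatment is 14 days on nominal visit days.
- With the ±2-day visit window, the Day 14 to Day 28 gap could reach (28 + 2) − (14 − 2) = 18 days.
- The interval from screening to Day 1 can still be 30 days, but Day 1 would then supply a current pre-dose value.

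**The case against.** The strongest objection is that the extra samples would be unlikely to detect the named risk. In the Japanese ADPKD subjects cited in the row, mean eGFR fell 18% on daprodustat and 21% on rhEPO by Week 52, from a daprodustat baseline of 10 mL/min/1.73m². If decline is assumed linear, six weeks corresponds to 18% × 6/52 ≈ 2.1%, or about 0.2 mL/min/1.73m². Creatinine at Days 14 and 28 could not resolve that. This stands as a limit on what the samples can show: they could reveal a large fall in an individual, not an average rate of cyst progression. It does not make the Appendix 7 sentence true.

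Other safeguards lower the stakes. Unscheduled safety samples are allowed (Section 9). Care is expected to follow KDIGO or an equivalent (Section 7.7.3). Impending dialysis is an exclusion, and the investigator may exclude anyone at unacceptable risk (Section 6.2) or stop treatment at discretion (Section 8.1). There is also no creatinine or eGFR stopping threshold, so more values would inform only that discretion. All of this is fair, but the row rests on the schedule, and none of these provisions schedules a measurement.

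The comparison with hemoglobin is imperfect. Those rows promise close monitoring, and hemoglobin drives dosing and stopping while kidney function drives neither. Four visits need not be the standard for kidney function, but a single value after the last planned dose still does not span the dosing period.

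Three smaller points also stand. The SAP (Section 10.4.1) counts the day after the stop date as on-treatment, so Day 42 is formally on-treatment for daprodustat; it is still one end-of-treatment value. The content of the Day 14 and Day 28 liver panel is inferred from Appendix 6, because the laboratory manual is not available. The SAP (Section 2.1) records that the study was terminated with 4 completed subjects, which limits the practical benefit of a change now.

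**Conclusion.** The concern holds. The mitigation stated for ADPKD cyst progression is not delivered by the schedule it cites: kidney function is measured at 1 of 4 planned treatment-period visits, on no planned daprodustat dosing day, and not for 41 days from Day 1. What exists is an end-of-treatment check plus one at follow-up.

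This should be corrected, but its weight is modest. Exposure is six weeks, the row itself reports no identified safety concern, and the primary endpoint is untouched.

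The conclusion assumes nominal visit days, no repeat of the Day 42 procedure (a repeat would extend dosing past the Day 42 sample), and a Day 14 and Day 28 liver panel without creatinine or urea.

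**What to change.** Add serum creatinine with calculated eGFR at three visits in the Schedule of Activities: Days 14 and 28, on the samples drawn for liver chemistry, and Day 1, on the sample drawn for lipids and hs-CRP. Change the copy of the schedule in SAP Section 10.2.1 to match.

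The cost is one analyte on blood already taken at three visits, a small laboratory charge and a few more results for the investigator to review. No extra visit or needle stick is needed.

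If the schedule is left alone, reword the ADPKD row of Appendix 7 to state what is done: kidney function is measured at screening, Day 42 and follow-up. That costs nothing and makes the text accurate, but it leaves the dosing period unmonitored by schedule.
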